#### **12.2.2.2 Concurrent Medications**

Number and percent of subjects in the FAS and in the PPS who took each individual concurrent medication and each class of concurrent medication will be provided.

#### **12.2.2.3 Safety Analyses**

Safety and tolerability endpoints will be summarized descriptively, based on the FAS. These summaries will be made in several ways in consideration of the varying durations of treatments: (1) for all subjects across the entire study; (2) by an appropriately chosen time segment, depending on the duration of therapy, e.g., by 3-, 6-, or 12-month intervals from start of therapy; and (3) by rates per patient year (i.e., %/year) or month.

#### **12.2.2.4 Demographic and Baseline Characteristics**

Demographic and baseline characteristics will be summarized across all subjects in the FAS, and across all subjects in the PPS. Continuous endpoints will be summarized by n, mean, median, minimum, maximum, and standard deviation. Categorical endpoints (includes binary endpoints) will be summarized by counts and percents per category.

## 12.3 Sample Size Determination

### • Initial CMML Cohort

The primary aim of the initial CMML cohort of this was to evaluate the ORR for tipifarnib in CMML subjects with KRAS/NRAS wild type (biomarker-positive subgroup, referred to below as "pos-subgroup"; and in CMML subjects with KRAS/NRAS mutations referred to as the "neg-subgroup"; those two subgroups comprise the entire population sampled in the trial. This trial is planned as a single treatment trial with statistical comparison to historical ORR rate 0.10 (10%). The statistical objective is to provide evidence that the TRUE underlying ORR in all subjects and/or in the pos-subgroup exceeds 0.10.

Prior data on tipifarnib in CMML subjects with unknown NRAS and KRAS mutational status yielded ORR~0.20. Nonclinically, it has been demonstrated using a large panel of cell lines that Ras wild-type cell lines are more sensitive to tipifarnib than Ras mutant lines (End 2001), therefore it could be possible that subjects without KRAS and/or NRAS mutations may be more sensitive to tipifarnib therapy. The availability of prior data suggest that use of Bayesian statistics, which can incorporate use of the prior information to yield more precise statistical estimates of response rates than traditional methods that rely only on data to be observed in the prospective trial. Thus, the probability that the TRUE underlying ORR exceeds 0.10 (i.e., success criteria) can be computed from the observed data, assuming a prior estimated TRUE ORR from the prior data. This probability is referred to as "posterior probability" in Bayesian analysis, since it is estimated from the observed data incorporating the prior estimate. If this probability is high (e.g., at least 0.80, i.e., meets the success criteria; probability of meeting the success criteria is referred to as "PoS"), then it can be concluded that the TRUE ORR exceeds 0.10, i.e., that the success criteria is met.

The probability that ORR exceeds 0.10 was computed for several potential scenarios to span the range of potential designs and design outcomes:

- Success Criteria: Probability that TRUE rate >0.10 is at least 0.80
- Assumed TRUE underlying ORR = 0.2, 0.3, 0.4 (0.2 useful for evaluating the entire population, 0.4 and 0.3 for evaluating the pos-subgroup)
- Sample Sizes: 10, 20
- Prior ORR = 0.3 (as a conservative estimate for the pos-subgroup)
- Prior data influence (measured by assumed sample size "N" that yielded the prior data)
  - = 1 (to minimize the influence of the prior data on the PoS estimate, i.e., to let the observed data drive the estimate), and
  - = 10 (to limit the influence of the prior data to an amount equal to the smallest reasonable sample size of observed data, which is N=10)

These probabilities are in [Table 7](#). For example, after ORR is observed in 10 subjects, if the TRUE ORR is 0.3, there is 0.85 PoS prior ORR estimate 0.3 with minimal (N=1) prior information; this result is highlighted in yellow in [Table 7](#). If the assumption on prior information is increased to N=10, PoS increases to 0.97, which is akin to over 95% power; this result is highlighted in green in [Table 7](#). PoS increases if TRUE ORR is higher (values for 0.4 are shown in [Table 7](#)), and decreases if TRUE ORR is lower (values for 0.2 are shown in [Table 7](#)). Thus, assessment using N=10 for the pos-subgroup yields sufficient power / precision based

on assumed ORR on par with prior AML data. [Table 7](#) also shows the corresponding values for N=7 for prior ORR based on N=1 and on N=7; NOTE that N=7 prior is used instead of N=10 since the prior assumption is given equal weight as the observed sample size.

**Table 7: Probability of success for various sample sizes**

Declare Success if prob.(TRUE rate>0.1) at least:	Prior Overall Response Rate Assumed	Probability of Success after N=10 if TRUE rate is:			Probability of Success after N=7 if TRUE rate is:		
		0.2	0.3	0.4	0.2	0.3	0.4
0.8	0.30 (N=1)	0.62	0.85	0.95	0.43	0.66	0.84
	0.30 (N=10 or 7)	0.9	0.97	>0.99	0.78	0.93	0.97

When assuming prior ORR=0.3 from prior N=10, observing at least 1 response from 10 subjects will meet the success criteria. When assuming N=1 for prior ORR=0.3, at least 2 responses from 10 subjects will meet the success criteria. For assumed prior from N=7, at least 1 responses from 7 subjects will meet the success criteria; for assumed prior from N=1, at least 2 responses from 7 subjects will meet the success criteria.

- **Amendment 3 Cohorts: MDS/MPN and AML**

The cohorts introduced in amendment 3 employ a 2-stage design. In the first stage, 28 eligible subjects (7 subjects per cohort in Stage 1) will be enrolled and stratified into one of four neoplasia and biomarker-defined cohorts based on diagnosis and subject CXCR4/2 expression ratio level (high vs low) determined from a bone marrow sample. Each cohort will be terminated if 0 responses are observed at end of first stage. Otherwise, an additional 11 subjects will be enrolled for the second stage.

At the completion of a two-stage cohort, the cohort will be considered as failed if there are 3 or less responses out of 18 evaluable subjects, indicating the true ORR is 10% or less. If there are 4 or more responses, the treatment will be considered of further interest indicating the true ORR is higher than 10%.

For this two-stage study design, a null response rate of 10% and alternative response rate of 30% are assumed. It provides 80% power to detect a difference between 10% and 30% ORR at one-sided significance level of 0.089. Using this design, the probability of terminating the cohort at the end of first stage is 0.48 if the true ORR is 10% or less while the probability of terminating the cohort at the end of first stage is 0.13 if the true ORR is 30%.

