## **STATISTICAL METHODS**

- **CML**

This initial trial cohort was planned as a single treatment trial with statistical comparison to historical ORR rate 0.10 (10%). The primary objective is to provide evidence that the TRUE underlying ORR in all patients and/or in the KRAS/NRAS wild-type subgroup exceeds 0.10. The evidence will be quantified by calculation of the Bayesian posterior probability that the TRUE underlying ORR exceeds 0.10 based on the OBSERVED ORR in the trial using both an informative and uninformative Bayesian prior distribution for TRUE ORR. If this probability

is over 80%, then it will be concluded that the TRUE ORR exceeds 0.10, i.e. the trial results will have met success criteria to demonstrate efficacy.

Prior data on tipifarnib in CMML (Study INT-28) yielded ORR ~0.20 in subjects with unknown KRAS/NRAS status. However, it is assumed that ORR in KRAS/NRAS wild type patients will be higher; hence, a Bayesian prior distribution with ORR=0.30 is assumed. The Bayesian prior will be given equal weight to the estimate from the trial, and, in order to be conservative, it will be evaluated with minimal weight of a single subject. If the TRUE underlying ORR for tipifarnib is 0.30, then a sample size of N=10 KRAS/NRAS wild type patients has ~85% probability to achieve the success criteria, assuming the minimally informative prior. Nonclinically, it has been demonstrated using a large panel of cell lines that Ras wild-type cell lines are more sensitive to tipifarnib than Ras mutant lines (End 2001), therefore it could be possible that subjects without KRAS and/or NRAS mutations may be more sensitive to tipifarnib therapy. If the TRUE ORR is 0.4, the probability of achieving success is 95%. Thus, the trial is adequately powered with N=10 KRAS/NRAS wild type subjects if the TRUE ORR in CMML is 0.4.

- **Amendment 3 Cohorts: MDS/MPN and AML**

The cohorts introduced in amendment 3 employ a 2-stage design. In the first stage, 28 eligible subjects (7 subjects per cohort in Stage 1) will be enrolled and stratified into one of four neoplasia and biomarker-defined cohorts based on diagnosis and subject CXCR4/2 expression ratio level (high vs low) determined from a bone marrow sample. Each cohort will be terminated if 0 responses are observed at end of first stage. Otherwise, an additional 11 subjects will be enrolled for the second stage.

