10.2 Efficacy analyses for the primary endpoint

The primary objective of the study is to assess the antitumor activity of tipifarnib. Objective Response Rate (ORR) will be estimated based on the crude proportion of subjects who achieve an objective response (as defined in section 10.1). ORR will be presented with a two-sided 95% confidence interval (CI) using the Clopper-Pearson method. For the CMMI subjects, Bayesian posterior probabilities that TRUE underlying rates exceed several meaningful levels of response rate (e.g., exceeding 0.1 for the primary endpoint ORR) will be computed. Informative and uninformative prior distributions of rates will be used. Traditional 90% confidence intervals for TRUE underlying rates will also be computed and reported.

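### CMML cohort: with the 0.30 prior weighted as 10 subjects, 1 response in 10 counts as success, and the 0.65 chance of this at a true ORR of 0.10 is not shown; the deciding prior and its weight are also unsettled

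*Protocol*

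**What the plan says.** Protocol 12.3 and SAP 5.3.1 compare the CMML cohort with a historical ORR of 0.10. Success requires a posterior probability of at least 0.80 that the true ORR is above 0.10. The prior is centred on 0.30 and given two weights, one subject or ten.

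- **Cut-offs.** For the heavier prior: "When assuming prior ORR=0.3 from prior N=10, observing at least 1 response from 10 subjects will meet the success criteria". With weight 1 the text asks for 2 of 10. For 7 subjects it gives 1 of 7 (weight 7) and 2 of 7 (weight 1).
- **Probabilities of success.** Protocol Table 7 and SAP Table 1 cover true ORRs of 0.2, 0.3 and 0.4 only. On moving from weight 1 to weight 10 at a true ORR of 0.3, the text says "PoS increases to 0.97, which is akin to over 95% power".
- **Which prior.** The synopsis plans the calculation "using both an informative and uninformative Bayesian prior distribution for TRUE ORR" and then tests one probability against 80%. SAP 10.2 says "Informative and uninformative prior distributions of rates will be used". Neither says what follows if the two disagree.
- **Which weight.** The synopsis gives the prior the same weight as the trial estimate and adds that "in order to be conservative, it will be evaluated with minimal weight of a single subject". Protocol 12.3 lists weight 10 as a scenario meant "to limit the influence of the prior data to an amount equal to the smallest reasonable sample size" of observed data, then explains that 7 replaces 10 for seven subjects because prior and data are weighted equally.

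**The concern.** A rule meant to show that the ORR exceeds 0.10 should seldom succeed when the ORR is 0.10. Under the heavier prior, an observed 0.10 is already enough. Power has meaning only beside an error rate, and none is given for this cohort, although the same section states a one-sided level of 0.089 against the same 10% null for the Amendment 3 cohorts. A reader who sets 0.97 beside the 80% power of those cohorts will take the CMML design to be the sharper one.

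Without a named deciding prior and a fixed weight, a borderline result could be reported as a success or a failure according to the prior chosen. That choice can still matter, because the published CMML counts are preliminary.

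**Working it through.** **Step 1: reproduce the plan's figures.** Inputs are the four printed cut-offs. With X binomial(n, p), the probability of success is P(X ≥ r).

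| Rule (prior weight) | p = 0.2 | p = 0.3 | p = 0.4 | Printed |
|---|---|---|---|---|
| ≥1/10 (10) | 0.893 | 0.972 | 0.994 | 0.9, 0.97, >0.99 |
| ≥2/10 (1) | 0.624 | 0.851 | 0.954 | 0.62, 0.85, 0.95 |
| ≥1/7 (7) | 0.790 | 0.918 | 0.972 | 0.78, 0.93, 0.97 |
| ≥2/7 (1) | 0.423 | 0.671 | 0.841 | 0.43, 0.66, 0.84 |

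All entries agree to within 0.013, so the rule has been read correctly and the 0.97 is right.

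**Step 2: the same calculation at p = 0.10.** No assumption about the form of the prior is needed.

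- ≥1/10: 1 − 0.9^10 = 0.651
- ≥2/10: 1 − 0.9^10 − 10 × 0.1 × 0.9^9 = 0.264
- ≥1/7: 1 − 0.9^7 = 0.522
- ≥2/7: 1 − 0.9^7 − 7 × 0.1 × 0.9^6 = 0.150

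Moving from p = 0.10 to p = 0.30 multiplies the chance of success by 0.972/0.651 = 1.5 under the heavier prior at N=10, and by 0.851/0.264 = 3.2 under weight 1.

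**Step 3: posteriors.** The documents give a mean and a weight m but no distribution. Assume Beta(0.3m, 0.7m). After x responses in n the posterior is Beta(0.3m + x, 0.7m + n − x). P(ORR > 0.10) is then:

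- m = 10: no data 0.947; 0/10 0.705; 1/10 0.885
- m = 1: 1/10 0.479; 2/10 0.815
- m = 7: 0/7 0.653; 1/7 0.882
- m = 1: 1/7 0.620; 2/7 0.907

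This form reproduces all four printed cut-offs. At 1/10 the two priors give opposite answers. That does not depend on taking the uninformative prior to be the single-subject one: Beta(1,1) gives 0.697 and Beta(0.5,0.5) gives 0.561, both below 0.80.

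**Step 4: effect of the weight.** Weight equal to the data lets 1/16 pass (0.900). At the 20 subjects planned for this cohort, weight 20 lets even 0/20 pass (0.81).

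**Step 5: results so far.** Both documents report 3/9 wild type and 0/7 mutant, hence 3/16 overall.

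| Result | m = 1 | m = 10 |
|---|---|---|
| 3/9 | 0.968 | 0.994 |
| 3/16 | 0.845 | 0.967 |
| 3/17 (hypothetical) | 0.822 | 0.960 |
| 3/18 (hypothetical) | 0.797 | 0.953 |

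**Step 6: the rule for all subjects and/or wild type.** Take 9 + 7 subjects and a true ORR of 0.10 in both subgroups. Under m = 1 the cut-offs are 2/9 or 3/16. With W wild-type and M mutant responses, success has probability P(W ≥ 2) + P(W = 1)P(M ≥ 2) + P(W = 0)P(M ≥ 3) = 0.2252 + 0.3874 × 0.1497 + 0.3874 × 0.0257 = 0.293. Under m = 10 the cut-offs are 1/9 or 2/16, giving 0.6126 + 0.3874 × 0.1497 = 0.671.

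**The case against.** The plan hides little. It prints both cut-offs and both rows of probabilities, calls the single-subject weight conservative, and rests its main claim on it: "85% probability to achieve the success criteria, assuming the minimally informative prior". The synopsis statement of adequate power uses the single-subject figures and is unaffected. The wording about using both priors could mean that both must exceed 0.80; then the stricter prior governs and 1/10 fails. SAP 10.2 adds "Traditional 90% confidence intervals for TRUE underlying rates will also be computed and reported", and for 1/10 a Clopper-Pearson 90% interval would run from 0.005 to 0.39, which nobody would take as evidence above 0.10. The cohort was enrolled before Amendment 3 and its result has been declared.

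Most of this stands and limits the severity. But the requirement for both priors is never written, and Protocol 12.3 says in its own right that 1/10 meets the criteria under the heavier prior. The intervals do not enter the success rule.

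Three stronger readings are tempting and not supported:

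- **The trial has a 65% false-positive rate.** That holds only if the weight-10 prior decides alone with ten subjects, and no section says it does.
- **The data cannot overturn the prior.** The weight-10 prior starts at 0.947, but 0/10 brings it to 0.705, a failure.
- **Every heavier-prior cut-off equals the historical rate.** 1/10 does; 1/7 is 0.143.

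**Conclusion.** The point holds as a fault in disclosure and in the decision rule. The table entries themselves are correct. Under the weight-10 prior, success is declared at the historical rate, with probability 0.65 when that rate is true. This figure is missing beside the 0.97, no deciding prior is named, and the informative weight is described in two ways.

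The 0.65, 0.52, 0.26 and 0.15 rest only on the printed cut-offs. The posterior figures rest on the assumed Beta form.

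A reader might infer that the reported success is an artefact of the prior. The documents do not support that: 3/9 passes with either weight. The all-subjects result is less secure. With three responses, the single-subject prior passes at 17 evaluable subjects and fails at 18, while weight 10 passes at both. The final evaluable count is not in the documents. Severity: minor to moderate.

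**What to change.** 1. **Protocol Table 7 and SAP Table 1.** Add a column for a true ORR of 0.10: 0.26 (weight 1) and 0.65 (weight 10) at N=10; 0.15 (weight 1) and 0.52 (weight 7) at N=7. Delete the comparison with power or put the 0.65 next to it.
2. **SAP 10.2.** Report posteriors under both priors. Base the success statement on a probability of at least 0.80 under the 0.30 prior with weight 1, computed at the final evaluable count and not from a fixed cut-off. State that this was set after preliminary results were known. Report the chance that the and/or rule succeeds at a true ORR of 0.10 for the final counts; it is about 0.29 if they stay at 9 + 7.
3. **Both documents.** Give the Beta parameters of both priors, say what the uninformative prior is, and reconcile the weight of 10 with the equal-weight wording. The meaning of uninformative is not a formality: at 1/7, Beta(1,1) passes (0.813) and Beta(0.5,0.5) does not (0.701).

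No new data are needed and no planned analysis is lost. The stated operating figures become less favourable. The deciding prior is named post hoc, although it is the stricter of the two, and its 0.26 (0.29 for the and/or rule) should not be presented as conventional error control.

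### The stated 0.13 probability of stopping a cohort at stage 1 when the true ORR is 30% should be 0.08

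*Protocol*

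**What the plan says.** Protocol section 12.3, under the Amendment 3 cohorts, describes one two-stage design that is applied to each of four cohorts. Stage 1 has "7 subjects per cohort in Stage 1". The futility rule is "Each cohort will be terminated if 0 responses are observed at end of first stage". A cohort with one or more responders continues, and then "an additional 11 subjects will be enrolled for the second stage". The final rule is that "the cohort will be considered as failed if there are 3 or less responses out of 18 evaluable subjects", so 4 or more responses count as success.

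On operating characteristics, the section says "a null response rate of 10% and alternative response rate of 30% are assumed". It then gives four figures:

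- Power and alpha: "It provides 80% power to detect a difference between 10% and 30% ORR at one-sided significance level of 0.089".
- Stopping under the null: "the probability of terminating the cohort at the end of first stage is 0.48 if the true ORR is 10% or less".
- Stopping under the alternative: the probability of "terminating the cohort at the end of first stage is 0.13 if the true ORR is 30" per cent.

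The same paragraph appears in the Statistical Methods part of the Protocol synopsis and in SAP section 5.3.2, with the same four figures.

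**The concern.** The stage 1 rule is so simple that its stopping probability is a single power: the chance that 7 independent subjects all fail to respond. At an ORR of 30% that chance cannot be as high as 0.13.

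The figure matters because it states the risk that the futility look closes a cohort in which the drug works as well as the design assumes. Anyone judging whether 7 subjects and a zero-response rule are acceptable would look at it. It also tells the reader how the design's 20% false-negative risk divides between the two stages. Because it stands in the synopsis, the protocol body and the SAP, it could pass unchanged into the study report.

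**Working it through.** **Inputs** (Protocol section 12.3): stage 1 size 7; stop if 0 responses; 11 further subjects, 18 in total; success if 4 or more of 18 respond; null ORR 0.10; alternative ORR 0.30. Responses are treated as independent with a common probability p.

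**Formulas**

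- Probability of stopping at stage 1: S(p) = (1 − p)^7.
- Probability of success: R(p) = P(at least 4 of 18) − S(p) × P(at least 4 of 11). The second term removes the sequences that would have reached 4 responses in stage 2 but were stopped because stage 1 had none.

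**Step 1: reproduce the figures that agree**

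- Null stopping probability: 0.9^7 = 0.4783. Stated 0.48.
- Alpha at p = 0.10: 0.0982 − 0.4783 × 0.0185 = 0.0893. Stated 0.089.
- Power at p = 0.30: 0.8354 − 0.0824 × 0.4304 = 0.8000. Stated 80%.

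These three agree to the precision given, so the paragraph was built on this exact binomial model with these stage sizes.

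**Step 2: the figure in question**

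- S(0.30) = 0.7^7 = 0.0824, which rounds to 0.08. Stated 0.13.

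The power calculation in step 1 uses 0.0824 as its stopping probability, and that is the value with which the stated 80% is obtained.

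**Step 3: look for a reading that gives 0.13 at an ORR of 30%**

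| Reading | Probability at ORR 30% |
|---|---|
| 0 of 5 | 0.168 |
| 0 of 6 | 0.118 |
| 0 of 7 (the plan's rule) | 0.082 |
| 1 or fewer of 7 | 0.329 |
| 1 or fewer of 10 | 0.149 |
| 1 or fewer of 11 | 0.113 |
| Passing stage 1, then failing at stage 2 | 0.118 |

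None gives 0.13. Holding the rule at 0 of 7 and changing the ORR instead, 0.75^7 = 0.1335, so 0.13 corresponds to an ORR of about 25%. Power at 25% is only 0.656, so the stated 80% belongs to 30% and not to 25%.

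**Step 4: compare with Table 7 of the same section**

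For the initial CMML cohort with the prior weighted as 7 subjects, section 12.3 says that 1 response in 7 is enough for success. Table 7 puts the probability of that at a true rate of 0.3 at 0.93, which leaves about 0.07 for 0 of 7. The exact values are 1 − 0.0824 = 0.918 and 0.082, so the table entry is itself off by about 0.01. Had 0.13 been right, the entry would have been 0.87. The section therefore gives two incompatible probabilities for the same event at the same rate. SAP Table 1 (section 5.3.1) and SAP section 5.3.2 repeat the conflict.

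**Step 5: size**

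- Absolute: 0.130 − 0.082 = 0.048. Relative: 0.13 / 0.0824 = 1.58.
- Two cohorts both at ORR 30%, each passing stage 1: (1 − 0.0824)² = 0.84, against 0.87² = 0.76 from the stated figure.
- Split of the 20% false-negative risk: 8.2% at stage 1 and 20.0 − 8.2 = 11.8% at stage 2. The stated figure would imply 13% and 7%.

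**The case against.** The arithmetic itself has no defence. The stage 1 size and rule are the same wherever the two documents give them, and 0.13 appears in both documents, so it is not an artefact of one page. Subjects without a post-baseline assessment are to be replaced, which keeps the denominator at 7; even losing one subject would give only 0.118.

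The fair objections concern weight.

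- **Nothing depends on the figure.** It is a reported property and feeds no rule. The stated 80% power already includes the true stage 1 loss: a single-stage test of 18 subjects would have power 0.835, so stopping costs about 3.5 points. A reader who relies on the power is not misled about the total risk of missing an active cohort. This stands.
- **The error is in the cautious direction.** The true risk of stopping an active cohort is lower than stated. This stands too.
- **The origin of 0.13 is unknown.** It equals the value at an ORR of 25%, but neither document uses 25% as an alternative for these cohorts. That it came from such a calculation would be inference.
- **The two-cohort example is only an illustration.** SAP section 4 limits the study report to CMML and MDS/MPN, and the working hypothesis is that response differs between high and low CXCR4/2 ratio. Both MDS/MPN cohorts being at 30% is not the expected case.

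These points limit the consequence. They do not make the figure right.

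**Conclusion.** The figure is wrong as written. Under the plan's own rule and its own alternative, the probability of stopping a cohort at stage 1 is 0.08, not 0.13: an overstatement of 4.8 percentage points, or 58% in relative terms. The result assumes only 7 evaluable subjects in stage 1, stopping on zero responses, and independent responses with a common probability of 0.30. The same assumptions reproduce the stated alpha, power and null stopping probability.

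It is a misreported operating characteristic and not a flaw in the design. Sample sizes, the futility rule, the threshold of 4 in 18, alpha and power stand, and no subject's treatment is affected. It should still be corrected, because it is the stated risk of wrongly closing an active cohort, it stands in three places, and it conflicts with Table 7 in the same section.

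**What to change.** Replace 0.13 with 0.08 in the Statistical Methods part of the Protocol synopsis, in Protocol section 12.3 and in SAP section 5.3.2. The cost is one number in three places; no other figure in that paragraph changes.

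Keeping 0.13 and labelling it as the value for an ORR of 25% would also be arithmetically correct, but it is weaker. It would bring in a response rate that is not the design alternative and leave the stopping probability at 30% unreported.
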